PROTOCOL

Background

1. Provide the scientific background, rationale and relevance of this project.

It is estimated that up to 24% of ovarian cancers, 8-10% of breast cancers, and 3-6% of uterine cancers are hereditary in nature[1, 2]. With implications for prognosis and treatment, the National Comprehensive Cancer Network and the Society of Gynecologic Oncology recommend universal genetic testing for all women with ovarian cancer and universal screening for Lynch syndrome in all women with uterine cancer[3, 4]. Additionally, these results have implications for a patient's family. In a patient with a germline pathogenic variant, first-degree relatives have a 50% chance and second-degree relatives have a 25% chance of carrying the variant.

Cascade testing describes directed genetic testing for first and second degree relatives of patients with known pathogenic genetic variants. It is well documented that despite the known importance of cascade testing for the prevention of cancer in unaffected individuals, there are several barriers to completion of cascade testing[5]. These barriers fall into two broad categories including informing at risk family members as well as family members acting upon this genetic information. Innovative models of testing, including cascade testing, was one of the recommendations made by the 2015 SGO Genetic Summit. Cascade testing for hereditary breast and ovarian cancer has also been identified by the CDC as a public health priority.

Before testing of relatives can occur, the proband (affected carrier) must disclose his or her status to family members. This process of disclosure can be difficult with barriers to disclosure including guilt, emotional distress, and complexity of genetic information, and there is evidence that while probands may discuss results with immediate family members, they will not share results with extended family, for whom the results may have consequences.⁷ Currently, physicians and genetic counselors rely on the patient to inform and educate family members regarding an identified pathogenic variant. At the time of disclosure of testing results, patients are currently provided a sample hard copy letter that they can send to their family members. However, further education regarding the pathogenic variant is left completely up to the patient.

We recently completed accrual for a pilot cascade testing trial to assess the outcomes following pre- and post-implementation of a research program designed to improve disclosure and cascade testing of women identified as harboring a pathogenic variant in ovarian cancer genes. Subjects were provided three communication aids, an informational brochure, a worksheet identifying at risk family members, and a template hard copy letter to share results. Women in the study found the materials both acceptable and useful, however cascade testing rates remained disappointingly low with only 6% of first degree relatives completing cascade testing. This confirms the need to evaluate novel approaches to education and testing of relatives.

Chatbots, also known as conversation agents, are programs designed to have interactive conversations with humans. While traditionally used in sectors such as online gaming and customer service, chatbots have made their way into a number of industries including healthcare and have shown promise in areas such as managing anxiety/depression, weight loss, and medication adherence. GIA (Genetic Information Assistant) is a chatbot specifically designed as a tool for patients to use for disseminating genetic results, education, and genetic counseling resources to their family members after they themselves receive a positive result.

Patients receive a secure GIA link from their provider and then are able to send their relatives the link to GIA through texting, email, and/or Facebook messenger. Once a relative clicks on the provided link, GIA's platform is structured as a decision tree, allowing family members to construct a personalized conversation about their family member's test results. This can be done either on a smartphone or computer. GIA provides basic genetics education and risk assessment and connects family members with local genetic counseling resources to continue this conversation and/or go forward with genetic testing. At the end of the conversation, the family member has the option of having a transcript sent to them via email for their reference. The objective of the current study is to evaluate the application of GIA for cascade testing in newly identified high risk breast and gynecologic mutation carriers.

Objectives/Hypothesis

The objective of this pilot study is to evaluate the feasibility and acceptability of GIA in sharing genetic test results with family members.

To determine the utility of GIA in sharing information.

To determine the impact of GIA on downstream cascade testing rates.

Study Design: Biomedical

1. Will controls be used? No

2. What is the study design?

Prospective cohort study.

3. Does the study involve a placebo? No

Human Participants

Ages: 18 and older

Sex: Female

Race: Any

Subjects- see below

INSTRUCTIONS: For question 1-4 below insert an exact #. Ranges or OPEN is not allowed. This # should be the maximum # you expect to need to enroll (i.e. sign consent) If you are only collecting specimens the number of participants should equate to the # of specimens you need. If you are collecting only data from a chart review the number should designate the number of subjects whose medical records you plan to review. Age/ Sex/Race criteria should designate the demographics of participants from whom you will obtain the specimen/data.

1. Provide target # of subjects (at all sites) needed to complete protocol. 20

2. Describe expected rate of screen failure/ dropouts/withdrawals from all sites. 10% attrition rate.

3. How many subjects will be enrolled at all sites? 20

4. How many subjects will sign a consent form under this UVa protocol? 20

Inclusion/Exclusion Criteria

1. List the criteria for inclusion

- Age \geq 18
- Undergoing genetic testing at UVA for a personal or family history of breast or gynecologic cancers in Cancer Genetics.

2. List the criteria for exclusion

- Not receiving treatment at UVA
- Not English literate
- Unable to provide consent

3. List any restrictions on use of other drugs or treatments. N/A

Statistical Considerations

1. Is stratification/randomization involved? No

2. What are the statistical considerations for the protocol?

Endpoints:

Determining the feasibility and acceptability of GIA in sharing genetic test results with family members will be evaluated through subject enrollment and use of the communication aid in sharing genetic results with family members. GIA allows for backstage analytics to follow objective metrics of family sharing, such as how many family members were informed, whether family members access a link, and what information family members prompted during their interaction with GIA. The utility of GIA in sharing information will be determined by collecting information about uptake and helpfulness of the aid (acceptability survey).

3. Provide a justification for the sample size used in this protocol.

This is a pilot feasibility study. Only descriptive statistics will be utilized and will be compared with historical controls.

4. What is your plan for primary variable analysis?

Enrollment number and accrual rate will determine feasibility, percentages will be used to determine uptake and use, as well as utility of the communication aid.

5. What is your plan for secondary variable analysis?

Percentages will be used to determine how many family members were informed, whether family members access a link, and what information family members prompted during their interaction with GIA.

6. Have you been working with a statistician in designing this protocol? No

7. Will data from multiple sites be combined during analysis? No

Study Procedures-Biomedical Research

1. What will be done in this protocol?

- 1) We will approach women while at a standard of care clinic visit in the Cancer Genetics for enrollment. Participants will be consented for the study with a written consent form, after having appropriate time to read the ICF and ask questions.
- 2) Participants will be sent a personalized, secure, GIA link to help them communicate testing to family members should they so choose. See the ***Clear Genetics Family Sharing Process*** document.
- 3) Participants will be sent an electronic Acceptability Survey to send back at their convenience via email
- 4) We will record the following from the subject's medical record: genetic testing results, family history, clinical demographics

2. If this protocol involves study treatment, explain how a subject will be transitioned from study treatment when they have completed their participation in the study. N/A

Bibliography

3. SGO Clinical Practice Statement: Screening for Lynch Syndrome in Endometrial Cancer [cited 2016 October 24]. Available from: <https://www.sgo.org/clinical-practice/guidelines/screening-for-lynch-syndrome-in-endometrial-cancer/>.

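### The cascade-testing objective has no described outcome: nothing in the endpoints, data sources or analyses is said to record whether relatives completed testing, and no denominator or time window is defined

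*Combined protocol and SAP*

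**What the plan says.** The protocol's Objectives/Hypothesis section sets three aims: feasibility and acceptability of GIA, its utility for sharing information, and "To determine the impact of GIA on downstream cascade testing rates".

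The endpoint paragraph (Statistical Considerations, item 2) takes up the first two. Feasibility and acceptability rest on enrollment and on use of the aid. It adds that "GIA allows for backstage analytics to follow objective metrics of family sharing, such as how many family members were informed", together with link access and the topics relatives asked about. Utility comes from the acceptability survey.

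The primary analysis (item 4) reads "Enrollment number and accrual rate will determine feasibility, percentages will be used to determine uptake and use", and adds utility. The secondary analysis (item 5) reads "Percentages will be used to determine how many family members were informed, whether family members access a link", and adds the information relatives prompted. Item 3 promises a descriptive comparison with historical controls but does not name the outcome compared.

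Study Procedures, item 1, gives the data flow. Step 3: "Participants will be sent an electronic Acceptability Survey to send back at their convenience via email". Step 4 takes from the subject's own record "genetic testing results, family history, clinical demographics".

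**The concern.** Two of the three objectives can be followed through to an endpoint and an analysis. The third cannot. If relatives' testing is not asked about at a planned time, an analyst cannot recover it afterwards.

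The metrics that are described do not answer this objective. The Background separates two barriers, informing relatives and relatives acting on what they learn. Sharing and link access speak to the first. For the second, the Background says GIA "connects family members with local genetic counseling resources to continue this conversation and/or go forward with genetic testing", which places testing after the described sharing steps. The earlier pilot shows that the two can diverge: its materials were well received, yet 6% of first-degree relatives completed testing. The risk is that this objective is reported empty, or that link clicks come to be read as testing uptake.

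**Working it through.** The plan gives no figure for this objective, so there is none to reproduce. The sample size of 20 is not derived from a testing rate. The main check is a trace of the objective through the plan.

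**Trace**

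- *Endpoints (Statistical Considerations, item 2):* enrollment, use of the aid, sharing analytics, survey uptake and helpfulness. No completed test by a relative.
- *Primary analysis (item 4):* enrollment, accrual, uptake, use, utility. None.
- *Secondary analysis (item 5):* relatives informed, link accessed, information prompted. None.
- *Data sources:* analytics, survey and the subject's record. None is described as recording a relative's test.
- *Denominator:* not defined. The Background describes cascade testing as covering first- and second-degree relatives, while the pilot's 6% is for first-degree relatives only. Neither is carried into an endpoint. Step 4 abstracts family history, which could help count relatives, but the protocol does not say it will be used that way.
- *Time window:* not defined. The survey comes back whenever the participant chooses, and the 6% has no stated window.

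**How precise could a rate be?** This bears on the choice of remedy; the gap does not depend on it.

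From the protocol: 20 enrolled and 10% attrition (Human Participants), giving 20 × (1 − 0.10) = 18; and the 6% (Background).

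Assumed, because the documents do not give them: the number of carriers, and 3 to 5 living adult first-degree relatives per carrier. A pathogenic variant is not an entry criterion, so carriers could be few. The Background's closing sentence speaks of mutation carriers, so the upper case is that all 18 are.

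- *1 to 4 carriers:* 1 × 3 = 3 to 4 × 5 = 20 relatives. Expected tested: 0.06 × 3 = 0.18 to 0.06 × 20 = 1.20.
- *All 18 carriers:* 18 × 3 = 54 to 18 × 5 = 90 relatives. Expected tested: 0.06 × 54 = 3.24 to 0.06 × 90 = 5.40.
- *No carriers:* also possible, and then there is no denominator.

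Exact (Clopper-Pearson) 95% limits for x tested of n are the 2.5% quantile of Beta(x, n − x + 1) and the 97.5% quantile of Beta(x + 1, n − x), with a lower limit of 0 when x = 0:

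| Tested / relatives | 95% interval |
|---|---|
| 0/3 | 0 to 70.8% |
| 1/20 | 0.1 to 24.9% |
| 3/54 | 1.2 to 15.4% |
| 5/90 | 1.8 to 12.5% |

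For 0/3 the upper limit is 1 − 0.025^(1/3) = 0.708. These intervals treat relatives as independent; clustering within families would generally widen them. They count first-degree relatives only, so they do not size the wider definition in the Background.

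**Why prior tests matter.** Participants may enter because of a family history, so some relatives may have been tested before GIA was shared. With assumed counts of 20 relatives, 2 tested before and 1 after, counting every test gives 3/20 = 15.0%. Counting only later tests among those not previously tested gives 1/18 = 5.6% (0.1 to 27.3%).

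**The case against.** The best defense is that the protocol is a short descriptive pilot and the missing pieces may sit elsewhere. The survey items and the Clear Genetics Family Sharing Process document are not reproduced, the analytics are introduced as examples rather than a full list, and family history is already abstracted. All of that stands. A reader might infer that relatives' testing will not be collected, or that no denominator could be built; the documents support neither. What remains is that, even if such data are captured, no endpoint, denominator, window or analysis is described that would use them.

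It might also be said that uptake already covers testing. The endpoint paragraph ties the word to GIA: "collecting information about uptake and helpfulness of the aid (acceptability survey".

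A third argument is proportion. With about one test expected at most in the low range, a new endpoint may not repay the effort. That is a fair reason to prefer deleting the objective, but not a reason to leave it in place with no outcome. Nor can one assert that later recall would be incomplete. The documents allow only that it could be, and that an unfixed survey time would make follow-up differ between participants.

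**Conclusion.** The point holds as a gap in description. One of three stated objectives has no described outcome, source, denominator, window or analysis. It should be fixed, preferably before follow-up begins, because a consistent window is hard to reconstruct later.

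The finding rests on the text alone. The carrier and relative counts are assumptions and serve only to show that any rate would be very imprecise, whichever range is chosen. A reader might go further and conclude that the pilot as a whole is compromised or underpowered. The documents do not support that: the primary aim has its own measures, the analysis is declared descriptive, and no power claim is made.

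**What to change.** Choose one.

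**(a) Define and collect the outcome.**

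- For participants with a pathogenic variant, record the date the result was disclosed and the date the GIA link was sent, and start the window at the later of the two. Study Procedures does not say whether the link follows the result, while the Background describes GIA as used after a positive one.
- At one stated time after that date, send survey items counting living adult first-degree relatives, those tested before the start date, and those who completed testing after it. Six months would be an example; it is an assumption, and the sponsor should set the time before follow-up begins. Ask about and report second-degree relatives separately. Cross-check the counts against the abstracted family history.
- Define the endpoint as first-degree relatives tested after the start date, divided by living adult first-degree relatives not previously tested. Add it to the endpoints, the secondary analysis and the procedures.
- Report it descriptively, with an exact interval and a note on family clustering. Reword the objective to *describe cascade testing rates among relatives of participants with a pathogenic variant*. Treat the 6% as context only, since there is no concurrent control and its exact denominator and window are not given.

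Cost: two recorded dates, a few survey counts, one extra timed email, edits to three sections, and a check on whether the consent wording needs updating. The data would be reported by the participant and possibly incomplete, and the rate very imprecise.

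**(b) Remove the objective.** Delete it from Objectives/Hypothesis and align the Background sentence that presents the study as evaluating GIA for cascade testing. In Statistical Considerations, item 3, name the outcome for the historical-control comparison or drop the comparison. State that sharing and link-access metrics are not evidence of testing uptake. Cost: text edits only, and the study then says nothing about testing uptake.

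### Feasibility rests on an enrollment count capped at 20 and an accrual rate with no period, denominator or benchmark, so the plan cannot estimate what share of the women approached consent

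*Combined protocol and SAP*

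**What the plan says.** The primary analysis (Statistical Considerations, item 4) reads: "Enrollment number and accrual rate will determine feasibility". The same sentence goes on to assign percentages to uptake, use and utility of the aid. The Endpoints paragraph under item 2 bases feasibility and acceptability on two things: enrollment, and use of GIA to share results.

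Under Human Participants, Subjects, the same figure is entered three times: "Provide target # of subjects (at all sites) needed to complete protocol. 20", "How many subjects will be enrolled at all sites? 20" and "How many subjects will sign a consent form under this UVa protocol? 20". The form's instruction for these entries is "This # should be the maximum # you expect to need to enroll (i.e. sign consent"). The only loss figure is in item 2: "Describe expected rate of screen failure/ dropouts/withdrawals from all sites. 10% attrition rate".

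On recruitment, step 1 of Study Procedures says "We will approach women while at a standard of care clinic visit in the Cancer Genetics for enrollment". Step 2 leaves use of the GIA link to the participant's choice. Step 4 lists what is taken from participants' medical records. No section gives a recruitment window, a time unit for accrual, a level of enrollment or accrual that would count as feasible, or any record of women approached, found eligible or declining.

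**The concern.** A feasibility measure should be able to distinguish a study that women join readily from one that most of them turn down. A count with a ceiling and no closing date does not do this, because it ends at the ceiling if recruitment goes on long enough. The second measure, accrual per unit time, depends on three things together: how many women attend, how many of those staff approach, and how many of those agree. Without the first two, the third cannot be separated out.

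This also affects the other results. The percentages for use and helpfulness are calculated among women who agreed to join a study of a chatbot link. If most women approached decline, those percentages describe a narrow group, and the report would have no means of saying so. Reasons for declining, such as having no email or smartphone or being reluctant to share, bear on whether the approach can work in this clinic. If they are not noted when the woman is approached, they are hard to reconstruct later.

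**Working it through.** **The plan's own figure.** The documents give no precision target, threshold or power for the 20, so no formula reproduces it. The only arithmetic available is attrition: 20 × (1 − 0.10) = 18 women remaining. The 10% is a single figure for screen failure, dropout and withdrawal. It is not a refusal rate among women approached and does not supply the missing denominator.

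**Inputs.** From the documents: the cap on consents is 20. Assumed for illustration, because the documents give neither: the consent proportion *p*, and the number of women approached per month *a*.

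**Enrollment number.** If recruitment runs to the cap, the number approached is 20 / *p* and the number declining is 20 / *p* − 20.

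| Consent proportion (assumed) | Approached | Declining | Enrolled | Exact 95% CI for the proportion |
|---|---|---|---|---|
| 80% | 20/0.80 = 25 | 5 | 20 | 59.3% to 93.2% |
| 40% | 20/0.40 = 50 | 30 | 20 | 26.4% to 54.8% |
| 10% | 20/0.10 = 200 | 180 | 20 | 6.2% to 15.0% |

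The intervals are Clopper-Pearson: with *x* = 20 and *n* approached, the lower limit is the 2.5% quantile of Beta(*x*, *n* − *x* + 1) and the upper limit is the 97.5% quantile of Beta(*x* + 1, *n* − *x*). They treat *n* as fixed. If recruitment stops at the 20th consent, *n* is the random quantity; the lower limit is unchanged and the upper limit falls slightly, so the intervals shown are a little wide.

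The enrolled column is the same in every row. The intervals do not overlap, so recording the denominator would separate these cases even with only 20 consents.

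**Accrual rate.** Consents per month = *a* × *p*.

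- With *a* held at 10 per month: 10 × 0.10 = 1 per month (20 / 1 = 20 months) against 10 × 0.80 = 8 per month (20 / 8 = 2.5 months). That is an 8-fold difference, so accrual rate does respond to willingness.
- With *a* ranging from 2 to 40 per month: the time to 20 consents runs from 100 down to 5 months at 10%, and from 12.5 down to about 0.6 months at 80%. The two ranges overlap.
- An observed 2 per month fits 0.10 × 20 approached and also 0.80 × 2.5 approached.

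Accrual rate therefore carries information on willingness only when the approach rate is known, and the plan does not record it.

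**The case against.** The strongest reply is that item 4 names two enrollment measures and the plan does not stop there. A reader might infer that the feasibility result would be identical however willing the women are. The documents do not support that: only the enrollment number is fixed by the cap, while accrual rate would differ 8-fold between 10% and 80% consent at a constant approach rate.

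A reader might also infer that feasibility cannot fail at all. That too goes beyond the text. The Endpoints paragraph counts use of the aid, and the chatbot's analytics record relatives informed and links opened. If 20 women enrolled and 2 shared the link, the plan would show it.

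A third tempting step is to read a refusal to join the study as a rejection of GIA, or to multiply consent by use to get a figure for all women approached. Neither is sound. Use is optional after consent, and a woman may decline a written consent form or a survey for reasons unrelated to the tool. In addition, GIA is described in the Background as a tool for use after a positive result, whereas the inclusion criteria admit women undergoing testing. Some of those approached may have no positive result to share.

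Finally, the ceiling comes from an institutional form that demands an exact maximum, and this is a small descriptive pilot. That explains the cap, but a small sample does not excuse the missing denominator, since the intervals above are informative at this size. What remains is that the enrollment component cannot be read as willingness, and that the percentages for use and helpfulness do not cover women who decline the study.

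**Conclusion.** The concern holds in a limited form. The enrollment number is bounded at 20 and gets there at any consent rate if recruitment continues. The accrual rate depends on both willingness and the flow of approaches, and has no stated period, denominator or benchmark. The plan therefore cannot estimate consent among approached eligible women, cannot say what enrollment result would count as feasible, and cannot show how selected the enrolled group is. GIA use among enrolled women is measured, and that part of the plan stands.

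On size, 20 consents are compatible with consent proportions as far apart as 80% and 10%. These proportions and the approach rates are assumptions chosen to show the range; the documents give no values. The conclusion about the count also assumes that recruitment is not closed before the cap is reached, and no closing rule is stated. This is worth correcting before recruitment because the remedy is cheap and the lost information is hard to recover.

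**What to change.** 1. In Study Procedures, step 1, add a de-identified tally of women approached, eligible, consenting and declining, with the reason for declining if the woman offers one.
2. In Statistical Considerations, item 4, make the enrollment component of feasibility the proportion of approached eligible women who consent, with an exact 95% CI, judged against a benchmark that the team sets before recruitment starts. Without the benchmark, the proportion alone would still not say what counts as feasible.
3. State a recruitment window and report consents per month over it as a supportive measure.
4. Keep study consent and GIA use as separate results, and report GIA use among enrolled women as already planned.

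The cost is a short amendment and a small tally kept by the staff who already approach women. No extra visits or participants are needed. The downside is a feasibility figure that may look less favorable than a bare statement that 20 women enrolled. If the window is also used as a closing date, recruitment could end below 20.
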